Aim 1: Analyses 1a-1c identify brain and psychological predictors of placebo analgesia, respectively. Placebo effects will be defined as Control vs. Placebo ([C – P]) differences in pain report (“placebo analgesia”) and two validated, pain-related brain measures: the NPS and SIIPS. These analyses will allow us to identify common and differential brain predictors of placebo effects on behavioral (pain report)

and neurobiological outcomes. They will permit three other novel tests: (1) Whether predictive patterns generalize across thermal and mechanical pain; (2) Whether they generalize across placebo effects in suggestion alone or post-conditioning; and (3) Whether we can identify latent factors across outcomes (thermal/mechanical, suggestion/conditioning), and develop predictors of those domain-general outcomes. Such factors are more likely to be genetically determined and useful in broader clinical contexts.

Multiple comparisons and power:

This study is the first large-scale study powered for *whole-brain analyses* of structural and functional correlates of placebo analgesia with Family-Wise Error Rate (FWER) map-wise correction. We will use FWER correction as implemented in Statistical Nonparametric Mapping (SnPM)⁴²³. This correction is valid, makes minimal assumptions, and is not affected by recent findings of inflated false positive rates with some correction methods⁴²⁴. With our sample size ($N = 600$), we have 80% power with whole-brain FWER correction to detect correlations with placebo analgesia of $r \geq 0.22$, which is within the range of our previous cross-validated estimates^{37, 268, 269, 353, 354, 369}.

Previous studies have been substantially underpowered; with $N = 50$, which is larger than most placebo studies, correlations must be $r = 0.65$ or larger to be detectable with 80% power. Though this is the first study adequately powered for whole-brain correction, we will also focus on testing hypotheses derived from the previous literature, as described below.

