[doi:10.1371/journal.pcbi.1004219] and VEGAS [http://dx.doi.org/10.1016/j.ajhg.2010.06.009] software tools. This set comprises 48 genes with an estimated 320 genotyped SNPs and 4800 imputed SNPs with MAF > .005. Most of these SNPs do not exist on the Affymetrix Axiom Precision Medicine chip, but they can be imputed with excellent fidelity from genotyped SNPs using the Haplotype Reference Consortium reference sequence database [doi:10.1038/ng.3643], which has replaced the 1kG reference database as the gold standard. This approach is now standard for GWAS. We estimate imputation of ~97% of candidate SNPs with ~99% accuracy using the *MACH* program⁴⁵⁸. **Power:** Assuming correction across ~50 candidate genes, we will have 80% power to detect effects of $d = 0.24$ ("small") or greater, substantially smaller than most previously reported associations. **Hypotheses:** Previous studies reported that opioid genes were related to fMRI signal in PAG and vmPFC⁴⁵⁹⁻⁴⁶¹; dopamine genes to enhanced placebo after conditioning, compared to suggestion alone^{462, 463}; and serotonin and CCK genes to (a) anticipatory activity in vmPFC, which correlates negatively with placebo analgesia^{63, 70, 464} and positively with anxiety⁴⁰⁸, and (b) activity in the serotonergic dorsal raphe nucleus (adjacent to the PAG), which is activated in placebo studies^{162, 403, 465, 466} and is linked to threat and analgesia in animal models⁴⁶⁷⁻⁴⁶⁹.

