Statistical learning framework for fMRI and molecular genetic analyses. In contrast to typical voxel-wise mapping fMRI analyses and SNP-by-SNP GWA analyses, multivariate predictive models predict outcomes as a combination of (pattern across) multiple voxels/SNPs. This model yields an aggregate predictive score based on all available brain/SNP information, which is validated by applying it to new individual test subjects. Placebo analgesia ($[C - P]$ in pain report) and changes in pain-related NPS and SIIPS responses ($[C - P]$) are the outcomes to be explained. We use LASSO-PCR⁴⁰⁸ or Least Absolute Shrinkage and Selection Operator⁵⁰¹ Principal Components Regression (Fig. 2; this compares favorably with popular support vector regression). *Data reduction:* principal components analysis retaining $N-2$ orthogonal predictors; *Penalized regression* of component scores onto the outcome uses LASSO shrinkage, simplifying the model. *Cross-validation* is five-fold, balanced cross-validation⁵⁰² in discovery sample ($N = 500$), with $N = 100$ reserved as a final test set⁴³⁵. These methods provide stable, robust estimates when there are more predictor variables (voxels or SNPs) than observations, and account for covariance among predictors (i.e., linkage disequilibrium in SNPs⁵⁰³). In addition, feature (variable) selection using our prior work on placebo analgesia⁴⁰⁸ will simplify the models and increase interpretability. *Tests of voxel and SNP importance* will be accomplished using a null-hypothesis permutation test^{408, 423, 504} ($p < 0.05$ FWER). In *molecular genetic* analyses, feature selection will be accomplished by (a) focusing on polymorphisms related to six key placebo-linked gene families, or (b) optimizing the inclusion threshold and sparsity⁵⁰³ via nested cross-validation.

Study timeline

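### The 5% family-wise error rate claimed for voxel and SNP importance in LASSO-PCR rests on an undefined permutation test, and under a natural reading it fails once any region truly predicts

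*Protocol*

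**What the plan says.** Protocol section IV, A.4, paragraph on the statistical learning framework, describes the model that predicts placebo analgesia and the placebo-related change in NPS and SIIPS responses. Data reduction is "principal components analysis retaining $N-2$ orthogonal predictors". The regression step "uses LASSO shrinkage, simplifying the model". Cross-validation is five-fold "in discovery sample ($N = 500$), with $N = 100$ reserved as a final test set". Testing of voxel and SNP importance "will be accomplished using a null-hypothesis permutation test", with a stated level of p < 0.05 FWER. For the molecular genetic models, one of two feature-selection options is "optimizing the inclusion threshold and sparsity" by nested cross-validation.

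The text does not state:
- which unit is permuted;
- which importance statistic is used;
- how the penalty is chosen for voxel models;
- whether tuning is repeated inside each permutation.

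A.3 (Multiple comparisons and power) plans a separate whole-brain analysis with SnPM family-wise correction. The SAP covers only the thermal pain ratings and says nothing about LASSO-PCR.

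**The concern.** The question asked is local: does this voxel or SNP matter? Shuffling the outcome over people produces a global null, in which no voxel or SNP is related to the outcome.

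For a one-voxel-at-a-time statistic the difference is harmless. The null distribution at an unrelated voxel does not depend on what happens elsewhere, so the maximum statistic controls family-wise error even when other voxels are truly related. A LASSO-PCR weight lacks this property. Each back-projected weight depends on every retained component and on the penalty, and a tuned penalty depends on whether there is anything to predict.

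Analyses 1a and 1b name systems that are expected to predict placebo effects, so a true signal somewhere is the working hypothesis. If the 5% level holds only when that hypothesis is false, a significant weight map shows that the model predicts something. It would nevertheless be reported as corrected evidence about particular voxels or SNPs. A check on null data would not reveal the fault.

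**Working it through.** **Inputs from the protocol.** Discovery N = 500; N-2 components; LASSO on component scores; five-fold cross-validation; level 0.05 (all A.4). A.3 gives r = 0.22 as a detectable correlation, used here only as an effect-size anchor: R² = 0.22² = 0.048. Analysis 2c gives "an estimated 320 genotyped SNPs and 4800 imputed SNPs".

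**Assumptions.** Outcomes are shuffled over unrelated people. One block of features carries the signal. R² = 0.10 and 0.25 complete the range. Feature counts and block structure are invented.

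**Model.** With orthogonal scores, and c_j the unpenalised coefficient of component j:
- b_j = sign(c_j) × max(|c_j| − λ, 0), with λ chosen by five-fold cross-validation.
- Weight map w = Vb, where V holds the component loadings.
- Threshold = 95th percentile of max|w| over permutations.
- Family-wise error is counted only over features outside the signal block.

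**The plan's own figure.** Under the complete null with λ re-tuned each time, the error was 0-7% in all designs (4.2% for 2,000 voxels, 3.3% for 4,800 SNP-like features). The stated 5% is reproduced there.

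**With one true region, λ re-tuned in every permutation:**

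| Design | Scores | Weakest | Middle | Strongest |
|---|---|---|---|---|
| A: 800 voxels, 20 networks | raw | 73% | - | 93% |
| A | standardised | 38% | - | 60% |
| A plus global signal | raw | 74% | - | 93% |
| A plus global signal | standardised | 30% | - | 59% |
| B: 2,000 voxels, 40 blocks | one scaling | 48% | 92% | 100% |
| C: 1,000 voxels, 25 blocks | raw | 49% | 89% | 98% |
| C | standardised | 17% | 39% | 88% |
| D: repeat, same N and component rule | raw | 52% | 92% | 100% |
| D | standardised | 6% | 44% | 76% |
| SNP-like: 4,800 features, 480 blocks | one scaling | 11% | 27% | 90% |

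B to D and the SNP-like case are at R² = 0.048, 0.10 and 0.25. Design A was indexed by the cross-validated r that the model achieved: 0.22 and 0.33 for raw scores, 0.10 and 0.24 for standardised scores (no global signal). Its raw and standardised rows are therefore not matched on signal. In B, 6%, 17% and 37% of all unrelated voxels were flagged. The Monte Carlo standard error √(p(1−p)/n) is at most √(0.25/500) = 2.2 points for B and √(0.25/120) = 4.6 points for A and the SNP-like case.

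**Mechanism.** Between 57% and 71% of permuted fits selected no component, so max|w| = 0 in those. With a share q of empty fits, the 95th percentile over all permutations is the (0.95 − q)/(1 − q) quantile of the non-empty ones: (0.95 − 0.57)/0.43 = 0.88 and (0.95 − 0.71)/0.29 = 0.83. Meanwhile the real fit loosens. In the SNP-like case it kept about 14, 33 and 139 components at the three signal levels, against about 6 with no signal. Back-projection spreads these over all features.

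**Other implementations, design B (R² = 0.048 / 0.10 / 0.25), plain weight as the statistic:**
- Observed λ reused in every permutation: 20% / 18% / 0.2%.
- 10 components kept: 6% / 12% / 41%.
- 50 components kept: 1.6% / 0.8% / 0.2%.
- No shrinkage: 4.6% / 2.4% / 0.2%.
- Voxelwise maximum correlation: 3.2% / 3.6% / 4.4%.

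Elsewhere, a reused λ gave 2-9% in A apart from one 20%. In C at the weakest signal it gave 23% (raw) and 5% (standardised), and in D 0-16%. Voxelwise permutation gave 3-7% in A, 5-7% in C and 2-4% in D.

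**A limit on the voxelwise test.** When design B was given a factor shared by all voxels, those outside the signal block became correlated with it. Re-tuned LASSO-PCR then flagged at least one in 29%, 69% and 100% of data sets, and a reused λ in 38% at R² = 0.10. The voxelwise test flagged at least one in 92% and 100% at R² = 0.10 and 0.25. For the voxelwise test these are true marginal associations, not errors, but they show what such a map can and cannot claim.

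**The case against.** The strongest reply is that A.4 commits to none of this. It does not say that outcomes are permuted, and it states nested tuning only for the genetic models, as one of two options. The sources cited for the test, one of which is also cited for SnPM in A.3, may define a procedure that cannot be seen here. The size of the problem depends on these choices: at R² = 0.048 in design B, the error runs from 1.6% to 48% according to the rule. The planned feature selection from earlier work was not simulated. All of this stands, and it is why the point is conditional.

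Three stronger readings are tempting and unsupported.
- *The plan's test has a 73-93% false-positive rate.* That describes one implementation under one assumed structure. SNP-like features gave 11% at the weakest signal.
- *The protocol expects a cross-validated r of 0.22.* A.3 gives 0.22 as a correlation detectable with 80% power at N = 600 under whole-brain correction, and says it lies within the range of earlier cross-validated estimates. It is not a forecast of model performance.
- *Aim 1 or the main analysis is invalid.* A.3 plans SnPM maps and hypotheses about named systems, A.4 also allows voxelwise mixed models, and the SAP's main analysis does not use LASSO-PCR.

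What the reply does not remove is the unconditional 5% claim. The no-shrinkage variant contradicts the stated LASSO, and a cut to 10 or 50 components contradicts the stated N-2.

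**Conclusion.** The concern holds in conditional form. A.4 asserts family-wise control at 5% for voxel and SNP importance without defining the null, the statistic or the penalty handling. If outcomes are permuted, that level is assured only when nothing predicts. Re-running the tuned model on shuffled outcomes is a natural reading, and under it the error over unrelated voxels was about 50-75% (raw scores) or 6-38% (standardised scores) at the weakest signals and about 60-100% at the strongest. For SNP-like features it was 11-90%. For features independent of the signal, a penalty held at its observed value gave about 0-23%, and no shrinkage gave 5% or less.

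These figures rest on assumed feature counts, block structure and effect sizes, and on unrelated participants. The direction and the mechanism were the same in every design with re-tuning. This goes beyond missing detail because the 5% statement would be wrong when Aim 1 succeeds, yet it is confined to the multivariate importance maps.

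**What to change.** Amend the statistical learning paragraph of A.4:

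1. State the permuted unit, the importance statistic and the penalty rule. Use outcome permutation to test overall model performance (cross-validated r), and limit any family-wise statement about weight maps to the global null.
2. Base family-wise corrected localisation on the voxelwise maximum-statistic (SnPM) analysis already planned in A.3, and on a SNP-wise equivalent. Describe the result as marginal association, and use permutations that respect twin pairs.
3. Label LASSO-PCR weight maps descriptive. Do not rely on a fixed penalty to restore 5%.

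The cost is wording, reuse of a planned analysis and one added SNP-wise permutation run. What is given up is any family-wise corrected claim about importance within the multivariate model, since a marginal test does not replace that. For comparison, a fixed penalty with standardised scores detected 0-1% of the truly predictive voxels in design A, against 37-97% for the voxelwise test.

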Brain and Genetic Predictors of Individual
Differences in Pain and Analgesia (Pain Genetics)

NCT03781570

Statistical Analysis Plan

2/13/2024

Statistical analysis plan

Our main statistical analysis will be focused on participants' thermal pain ratings in the placebo compared to the control condition (conditions are within participant). We will report the mean and standard deviation of the difference in pain rating for control minus placebo, across participants. We will test for significant differences with a mixed-effects model, controlling for the stimulus intensity, and using the standard a-priori statistical threshold of alpha = 0.05. To account for the familial structure of the dataset (which includes monozygotic and dizygotic twin pairs), we will include familial random effects in the model, modelled separately for monozygotic and dizygotic twins.

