Extensions and alternative plans. (1) We are developing new large-sample predictors of pain, and will test those as they become available. (2) Another important extension relates to individual differences in pain sensitivity. While not the main focus here, this dataset and our approaches are well-suited to predicting individual differences in pain sensitivity—a core feature of many pain conditions⁴⁴¹⁻⁴⁴³ and a risk factor for later chronic pain⁴⁴⁴⁻⁴⁴⁶. Models of risk for chronic pain following surgery (unfortunately common) and other procedures would be a crucial advance in precision medicine⁴⁴⁷⁻⁴⁵². Risks can be assessed at both phenotypic (predicted by evoked pain sensitivity) and genetic⁴⁵³ levels. Exploratory analysis will allow us to develop a foundation for understanding the neurobiology of individual differences in pain sensitivity.

Aim 2: Analyses 2a-2c will assess the heritability of placebo effects and placebo-predictive brain features, and relate these features to candidate gene families. **Analysis 2a (Aim 2.1)** identifies the heritability of placebo effects in pain report and brain responses for the first time. We hypothesize that heritability of pain reports will be modest, but heritability of placebo modulation of specific pain-related brain measures (the NPS and SIIPS) will be stronger, as these reflect component systems that are less etiologically complex and less context-sensitive than overall pain report. We also expect heritability to be high for gray-matter density in nAC and hippocampus⁴⁵⁴, and mPFC-brainstem pathways. The **model** for analysis 2a is a standard univariate ACE model^{455, 456}, which decomposes twin covariances for a trait of interest into additive genetic (A), shared environmental (C), and non-shared environmental (E) variance

components (Fig. 5). This model will be applied to individual placebo measures (e.g., thermal and mechanical pain), and also to latent variables (i.e., using a common factor model with thermal and mechanical pain loadings constrained to equality to identify the factor).

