There are four main phases during fMRI: In the placebo administration phase, participants are given two identical creams with different instructions: "Procaine, an effective pain-relieving drug" (Placebo) and "a control cream with no effects" (Control) applied to 2 fingers each on each hand, with locations counterbalanced across subjects. Disclosure of side effects are presented on forms with realistic-looking drug company logos (see attachment 'drug_info_packet_script_PAIN-GEN'), and testing is done in a medical environment with medical equipment and related context cues. A 10-minute delay follows for the "cream to take effect", during which we will collect structural (T1-weighted) images. A suggestion-only test phase will test thermal and mechanical pain delivered to fingers on and off treatment with a placebo analgesic cream. Placebo effects will be defined as within-person Control vs. Placebo ([C – P]) differences in pain report ("placebo analgesia") and brain activity. A conditioning phase follows, with delivery of high- and low-intensity stimuli on placebo- and control-treated skin sites, respectively^{383, 410-412}. This reinforcement strengthens expectations^{383, 410-412} and induces non-conscious learning^{24, 234, 413}. To limit testing to one session, structural (T1 and diffusion-weighted) images will be collected during behavioral conditioning. A post-conditioning test phase tests both pain types on and off placebo treatment after reinforcement. We have successfully used similar procedures⁴¹⁴, as have others²²² (e.g., C. Büchel, $N = 700$ with suggestion-alone and post-conditioning, no imaging) Rating scale: Ratings of pain intensity and

affect will be made after each trial on a 100-point generalized visual analogue scale⁴¹⁵⁻⁴¹⁸ with anchors of “no pain” and “most intense sensation imaginable,” using an fMRI-compatible trackball²²¹.

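### Does the SAP's one test need changing because it names only familial random effects and leaves the unit of analysis and the condition slopes unstated?

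*SAP*

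**What the plan says.** The SAP is one paragraph. The outcome is the thermal pain rating under placebo and under control, and both conditions are observed in every participant. The descriptive result is the "mean and standard deviation of the difference in pain rating for control minus placebo, across participants". The inferential step reads: "We will test for significant differences with a mixed-effects model, controlling for the stimulus intensity", at alpha 0.05. The family structure enters through one clause: "we will include familial random effects in the model, modelled separately for monozygotic and dizygotic twins".

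For this test the SAP does not state the unit of analysis, a participant effect, or whether the familial effects are intercepts, slopes on condition, or both.

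The protocol gives context but no model for this test. Section A.3 (Aim 1) says "Placebo effects will be defined as Control vs. Placebo" differences in pain report and in two brain measures. Section A.4, in the statistical learning framework, says that the control-minus-placebo contrasts in pain report and in those brain measures "are the outcomes to be explained". Section A.2.2 gives 32 test-phase trials over four conditions, hence 8 heat trials on placebo and 8 on control, with a rating after each trial. Section A.4 allows for correlated errors between twins only in the second-level voxelwise imaging model.

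**The concern.** The tested quantity is a contrast within person, and the study exists because that contrast differs between people. Aim 2 "identifies the heritability of placebo effects in pain report and brain responses for the first time", which presupposes such variation. The standard error of the mean contrast must therefore carry the between-person and between-family variance of the effect.

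A random intercept does not do this. With trial ratings as rows, a participant or family intercept shifts both conditions equally and cancels from the contrast. The variation in the effect is left in the residual and diluted by the far more numerous degrees of freedom of trial noise. Ratings are recorded trial by trial, and an intensity covariate suggests a rating-level model, so such a fit is conceivable. Since this is the SAP's only test, its interval and p-value would be affected.

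**Working it through.** **Inputs from the documents.** 600 twins in 300 pairs (Protocol Section IV); 8 heat trials per condition (A.2.2); alpha 0.05, taken as two-sided. Section VII gives 700 twins, but the ratios of standard errors below do not depend on the number. The plan gives no figure for this test to reproduce: no SD, effect size or power.

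**Assumed inputs, none of them in the documents.** t = SD of individual effects, 3 to 15; s = trial SD, 15; w = within-family person SD, 10 to 20; r = twin correlation of effects, 0.3. All are in points of the 100-point scale.

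**Variance of the mean control-minus-placebo difference.**

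- True: [4t²(1+r) + s²]/2400.
- (1) Trial rows, participant intercept, no slope: [s² + 0.266t²]/2400. The residual pools 599 df of person-by-condition variation with 8,400 df of trial noise, and 0.266 = 4 × 599/8,999.
- (2) Trial rows, family intercept only: [s² + 0.516w² + 0.258t²]/2400.
- (3) Condition means, participant intercept: [t² + s²/4]/600.
- (4) Condition means, family intercept only: [s²/4 + 1.335w² + 0.666t²]/600.
- (5) One difference per participant with a family intercept, or trial rows with intercepts and condition slopes for both participant and family: estimates the true variance.

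**Worked example, t = 10, w = 15, s = 15, r = 0.3.**

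- True: (520 + 225)/2400 = 0.3104, SE 0.557.
- (1): (225 + 26.6)/2400 = 0.1048, SE 0.324.
- (2): (225 + 116.1 + 25.8)/2400 = 0.1529, SE 0.391.
- (3): (100 + 56.25)/600 = 0.2604, SE 0.510.
- (4): (56.25 + 300.4 + 66.6)/600 = 0.7054, SE 0.840.

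Actual type I error is 2[1 − Φ(1.96 × model SE/true SE)]:

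| t, w | (1) | (2) | (3) | (4) |
|---|---|---|---|---|
| 3, 20 | .073 | .013 | .055 | .000 |
| 3, 10 | .073 | .047 | .055 | .001 |
| 5, 15 | .113 | .052 | .061 | .000 |
| 10, 15 | .255 | .169 | .073 | .003 |
| 15, 10 | .376 | .337 | .078 | .053 |

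Simulation agreed with the closed forms to within .016. The forms in (5) gave .047 to .055.

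**Family intercepts plus family condition slopes on trial rows.** The SAP's wording permits this without any added term. Simulated type I error was .053 at (t, w) = (10, 15), .055 at (8, 15), .052 at (15, 10), about .03 at (5, 20) and .015 at (3, 20). It departs from 5% materially only when t is below about 0.32w, and then on the conservative side.

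**When the verdict would differ.** In the example, significance needs an estimate above 1.96 × 0.557 = 1.09 with the correct SE, 1.96 × 0.324 = 0.64 under (1) and 1.96 × 0.391 = 0.77 under (2). Only estimates of about 0.6 to 1.1, or 0.8 to 1.1, would be called differently.

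**A check that readers can make.** The SAP already reports the SD of the participant differences. In the example it is √(100 + 2 × 225/8) = 12.5, so 12.5/√600 = 0.51, which equals (3) and misses only the twin correlation. A model SE of 0.32 beside that SD would look wrong at once.

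**Intensity covariate.** Under A.2.2 test-phase heat is one level, so the covariate is constant there. Pooling test and conditioning trials with a linear intensity term (assuming 8+8 conditioning heat trials) gives a condition estimate equal to the test-trial difference. The covariate does not alter the picture.

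**The case for a change.** The strongest case for a change is that this is the only test in the SAP and that the readings its wording leaves open give standard errors from 0.32 to 0.84 in the example. The intensity covariate points towards ratings as rows, and a sentence or two would settle the matter. The algebra behind this stands: intercept-only models on trial ratings are too optimistic with a participant intercept whenever effects vary between people, and they err in either direction with a family intercept alone. Stating the unit would be good practice.

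Three things weaken it. First, the largest error rates (7.3% to 37.6% in the range above) belong to a model with a participant intercept and no slope; the SAP names no participant term, so that model has to be supplied before it can be faulted. Second, the SAP speaks of familial effects without limiting them to intercepts, and the slope version holds its level or is conservative. Third, if each participant contributes one difference, familial effects are the only random effects required, which is exactly the set named. That agrees with the summary across participants and with the contrast defined in A.3 and A.4. Section XI repeats the definition, but in a paragraph whose procedure differs from other parts of the protocol, so it carries little weight. The covariate does fit the participant-level reading less well, and that part of the objection remains.

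**Conclusion.** The SAP leaves a detail unstated; it does not prescribe a wrong analysis. At least one natural reading is valid, another that needs no added term is nearly so, and the protocol's definition of the effect points to the first. Writing the structure down would record a reading that the text already permits.

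The possible harm is wrong interval width and p-values under intercept-only fits to trial ratings, with a changed verdict only for mean effects of roughly 0.6 to 1.1 points out of 100 in the example. The analyses for Aims 1 to 3 have their own models and do not rest on this test. That intercept-only fits misstate the error is certain given variation in the effect. How far they do so rests wholly on assumed trial, person and effect SDs and an assumed twin correlation, since the documents give none. No change follows.
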